Total knee arthroplasty (TKA) is among the most common surgical procedures performed in the US^{1,2}, and as the population ages and face age-related joint deterioration, will only increase in frequency.^{3,4} Although in the majority of cases, patient-centered outcomes (pain, function and quality of life) are improved following this procedure, a significant number of patients develop chronic post-surgical pain (CPSP), which is often rated as severe, and includes treatment-resistant neuropathic components.⁵ The International Association for the Study of Pain defines CPSP as pain that develops or increases in intensity after a surgical procedure, persists beyond the tissue healing process (> 3months), and is localized to the surgical field or innervation territory of nerve located in surgical field.²⁴ Rates of CPSP are alarmingly high following TKA, with Petersen and colleagues^{6,7} reporting that between 44% to 53% patients develop CPSP, 15% to 19% of whom rate their pain as severe. Clearly, the development of CPSP following TKA is a significant adverse outcome, which brings with it decreased quality of life, diminished functionality, disability, and perhaps most concerning in the era of the opioid crisis, long-term opioid use.^{8,12} Further, CPSP is associated with notable economic burden, with recent analysis suggesting almost \$30,000 in annual adjusted indirect costs to patients per year, an amount directly related to the severity of CPSP pain.¹³

Preoperative Predictors of Chronic Post-surgical Pain

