For the second study objective, we expect that participants, who receive a MI intervention along with a validated computer-assisted CBT intervention for chronic pain (PAINTrainer) will demonstrate a significantly greater improvement in outcome variables from baseline vs those receiving usual care. The outcome variables will include change in the severity of pre-operative chronic pain, opioid use, and psychological risk factors (depression, anxiety, catastrophizing) for CPSP in the 4 weeks prior to surgery. Specifically, a mixed model analysis will be fit to the data using the Proc Mixed procedure in SAS.^{56,57} Residual modeling will be performed to check for significant violations in the distribution and constant variance assumptions and determine if variance stabilizing or normalizing transformations should be applied. Furthermore, sensitivity analyses will be run considering dichotomous versions of the outcome variables using multiple logistic regression.

For the third study objective, we will describe the effects of the CBT intervention on 72hr post-operative pain severity, and 3- and 6-month rates of CPSP in comparison to patients who received treatment-as-usual. A mixed effects model will be fit with Treatment Group (intervention and usual care) as a between subject factor and Time (72hr, month 3 and 6) as a categorical within-subjects factor. We will include as baseline covariates any factors that differ significantly between the groups at baseline or show significant relationships with the outcome.

Potential confounders (medical comorbidities, post-operative complications) will also be considered in the analysis.

The results from the mixed model analyses will be summarized by mean (SE) change from baseline for each group at each time point. The primary hypothesis will be evaluated at the alpha = 0.05 level and all contrasts/hypotheses will be considered exploratory and results will be interpreted with caution at alpha equal to 0.05 level. The primary goal will be to obtain reliable effect size estimates to inform larger studies. In that women are more likely to develop CPSP than men,^{8,16} sex as a biological variable will be considered as a possible moderator in all analyses.

RISK/BENEFIT ASSESSMENT:

1. Risks:

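### Objective 3's single mixed model (Time = 72hr, month 3, month 6, reported as change from baseline) does not fit the scheduled data for 72-hour VAS or CPSP, and no link, distribution or effect measure is given for CPSP

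*Combined protocol and SAP*

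**What the plan says.** All references are to the combined protocol and SAP.

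- **Outcomes.** Study Procedures, 5. Statistical Analysis, says for the third objective: "we will describe the effects of the CBT intervention on 72hr post-operative pain severity, and 3- and 6-month rates of CPSP", compared with usual care.
- **Model.** The next sentence fits one mixed effects model with treatment group "as a between subject factor and Time (72hr, month 3 and 6) as a categorical within-subjects factor". It names no response variable, distribution or link. Covariates are to be "any factors that differ significantly between the groups at baseline or show significant relationships with the outcome", and post-operative complications will also be considered.
- **Summary.** After both objectives: "The results from the mixed model analyses will be summarized by mean (SE) change from baseline for each group at each time point".
- **Purpose.** "The primary goal will be to obtain reliable effect size estimates to inform larger studies". The sample-size text (1. Target Population and Accrual) likewise calls the CPSP analysis exploratory and meant to yield effect sizes.
- **Definition.** The Background takes CPSP to be "pain that develops or increases in intensity after a surgical procedure, persists beyond the tissue healing process (> 3months", located in the operated area.
- **Measurement.** Under 1. Study Instruments, post-operative severity has two components: VAS ratings every 4 hours, reduced to an area under the curve (AUC), and opioid consumption over 72 hours. CPSP comes from a checklist at 3 and 6 months.
- **Other methods for binary data.** In the Objective 2 paragraph, "sensitivity analyses will be run considering dichotomous versions of the outcome variables using multiple logistic regression". Another logistic regression serves baseline comparisons. The Study Design section says only that CPSP group differences will be inspected.

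**The concern.** A repeated-measures model with a three-level Time factor needs one response that is observed at those times, and a change-from-baseline summary needs a baseline value. Neither 72-hour VAS nor CPSP appears to meet these conditions, and CPSP is binary.

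CPSP is the outcome that the intervention is meant to prevent. If its model and effect measure are not fixed, the choice among risk difference, risk ratio and odds ratio can be made after the data are seen, and a larger trial may be planned on the result.

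**Working it through.** The plan gives no figure for this analysis, so the check sets the model beside the schedule (Methods, 4. Administration of Surveys and/or Process).

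**Step 1. Time levels that hold data**

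| Measure | Baseline | 72hr | Month 3 | Month 6 | Levels of Time filled |
|---|---|---|---|---|---|
| 72-hour VAS | no | yes | no | no | 1 of 3 |
| 72-hour MEDD | no | yes | no | no | 1 of 3 |
| CPSP checklist | no | no | yes | yes | 2 of 3 |
| Usual opioid use (MEDD) | yes | no | yes | yes | 2 of 3 |
| BPI | yes | no | yes | yes | 2 of 3 |

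**Step 2. What the model can estimate.** Group by Time has 2 × 3 = 6 cell means. VAS supplies 2 × 1 = 2 of them and CPSP 2 × 2 = 4. The empty cells are empty for every patient by design, so no missing-data assumption fills them. For CPSP the gap is also logical: pain defined as persisting beyond 3 months cannot be present at 72 hours.

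**Step 3. Could some other response fit?** Consumption is recorded in 24-hour increments as well as in total, so a daily MEDD within the 72 hours could be joined to usual daily MEDD. That gives 2 × 3 = 6 cells and a baseline. The plan does not name this response. It would mix acute post-operative consumption with usual use, and it does not estimate CPSP rates. Joining VAS to BPI intensity is further off: it crosses two instruments and depends on Step 6.

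**Step 4. Is CPSP analysed elsewhere?** No. One logistic regression belongs to the dichotomized Objective 2 outcomes and the other to baseline comparisons. The Study Design sentence gives no method.

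**Step 5. Does the effect measure matter?** Assume, for illustration only, CPSP in 50% of controls and 30% of intervention patients. The risk difference is 0.50 − 0.30 = 20 points, the risk ratio 0.30/0.50 = 0.60, and the odds ratio (0.30/0.70)/(0.50/0.50) = 0.43. The same data give three different numbers to carry forward.

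**Step 6. Follow-up BPI.** The Preoperative chronic pain paragraph and the schedule place BPI at 3 and 6 months without condition, and the Appendix starts the checklist from the BPI result. The Chronic post-surgical pain paragraph, 6. Subject Follow-up and 1. Detailed Description give the BPI only if CPSP is present. The Background cites reports that "between 44% to 53% patients develop CPSP". At those rates a conditional BPI would cover 0.44 × 75 = 33 to 0.53 × 75 = 39.75, about 40, of 75 controls. The number in the intervention arm is unknown. A comparison would then be confined to a subgroup formed after randomization.

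**Step 7. Scale of the 72-hour AUC.** At one rating per 4 hours, 72 hours give 72/4 = 18 ratings. Patients discharged early switch to a daily diary. Assuming one diary rating per day, discharge at 24 hours leaves 24/4 + 2 = 8 ratings, and at 48 hours 48/4 + 1 = 13. A raw AUC is comparable across patients only if it is standardized for the time covered.

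**The case against.** The strongest reply is that this is compressed drafting. The sentence before the model names the outcomes, and the Time levels may simply be pooled in one parenthesis: 72hr for pain severity, months 3 and 6 for CPSP. Unlike the Objective 2 text, the sentence does not name Proc Mixed, so a generalized mixed model is not excluded. The change-from-baseline sentence follows both objectives and may be meant only for measures that have a baseline. CPSP is exploratory, the protocol calls the study a small pilot, and published counts by arm and visit would let readers compute any unadjusted effect measure.

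Much of this stands. A logistic mixed model may have been intended, and the exploratory status limits the harm. But even a logistic model could not use the 72hr level for CPSP or report its change from baseline, and the pooled reading still leaves link, distribution and effect measure open. Exploratory status does not supply an estimator when estimation is the stated goal. Published counts would not settle the adjusted, repeated-measures estimate.

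**Conclusion.** The point holds and should be fixed. As written, the Objective 3 model cannot be applied to 72-hour VAS (1 of 3 Time levels, no baseline) or to CPSP (2 of 3, no baseline), and no other section supplies a CPSP model. The finding rests on the schedule and the protocol's definition, not on a numerical assumption. The consequence is limited to the effect estimate carried to larger studies.

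A reader might infer more than the documents support:

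- **Bias or lost power.** Too little of a model is stated to compute either.
- **Imprecision of the CPSP estimate.** The width of its confidence interval follows from 75 per arm and would be much the same after the fix, so it does not measure this defect.
- **A mixed model rules out binary data.** The text does not say so.
- **No opioid measure could use the Time factor.** Daily MEDD nearly can.
- **Follow-up opioid use is recorded only in patients with CPSP.** That is one possible reading of 6. Subject Follow-up and 1. Detailed Description, but the Study Instruments text asks about opioid use regardless of CPSP. Only the BPI conflict is clear.

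**What to change.** Replace the single Objective 3 model with:

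1. **72-hour outcomes.** Separate between-group linear models for the 72-hour pain summary and for 72-hour MEDD, each adjusted for baseline pain and baseline MEDD. Keep the AUC, but put it on a scale that stays comparable when diary ratings replace 4-hourly ratings, for example AUC divided by hours covered.
2. **CPSP.** A binary repeated-measures model at 3 and 6 months (GEE or a logistic mixed model) with group, time and group-by-time, reporting the between-group risk difference with 95% CI at each visit. With 10% attrition expected, state the missing-data assumption: standard GEE needs a stronger one than a likelihood-based mixed model. A logistic mixed model must be averaged over patients to give a risk difference.
3. **Change from baseline.** Report it only for measures that have a baseline.
4. **Post-operative complications.** Keep them out of the main treatment-effect models, because they arise after randomization.

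Separately, before any longitudinal BPI comparison, reconcile whether follow-up BPI is collected from all patients or only from those with CPSP.

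The cost is rewording and a little more programming; items 1 to 4 need no new data. If BPI is reconciled to all patients, it is added to calls with patients without CPSP. The protocol already allots 30 minutes to each follow-up.

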A power analysis was conducted for the post-operative pain outcomes; being a novel intervention, opioid taper outcomes were not considered. Estimated group means, variances, and effect-size were drawn from the literature.^{41,42} The sample size estimate was derived for the primary outcome variable, chronic pain severity, using an expected baseline mean of 4.82 (Effect size: 0.33). Based on estimates obtained, a sample size of 75 participants provides 80% power to detect a pre-post improvement in pain severity (14.5%), depression (21.3%), anxiety (24.3%), and catastrophizing (29.5%), statistically significant at alpha of 0.05. Being a novel intervention, the analysis for chronic post-surgical pain will be considered exploratory and used to obtain effect size estimates. We anticipate a low attrition rate (10%) and will over-recruit 16 additional participants (total 83 subjects per group) to retain adequate power.

2. Key Inclusion Criteria:

[figure not shown]

Figure 1. Predictive factors of CPSP following TKA

1. Males and females, age > 21 years
2. Chronic non-malignant pain of at least 3 months duration
3. Morphine equivalent daily dose (MEDD) > 50 milligrams for at least 3 months
4. Able to enroll at least 4 weeks prior to planned surgery
5. Able to speak, read and comprehend in English at the 6th grade or higher proficiency

Participants will be selected so as to represent the gender, ethnicity, and age of the patient population of individuals seeking TKA in greater Philadelphia area, thus the sample is expected to be 50% women, 55% white, 35% African-American, 6-8% Latino, and 2-4% other or multiracial, and on average 67 years of age. No restrictions on gender or ethnicity will be applied. Because total knee arthroplasty surgery is uncommon in children, individuals under the age of 21 will not be included in this proposed study.

3. Key Exclusion Criteria:

1. Pain of malignant origin
2. Current or past history of opioid use disorder (including those on medication-assisted therapy)
3. Revision of TKA
4. Comorbid CNS disease such as dementia, HIV, psychosis, poorly controlled bipolar disorder or any condition interfering with informed consent

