STUDY DESIGN:

A randomized clinical trial is proposed to evaluate the efficacy of the novel computer-assisted preoperative CBT/opioid sparing intervention to affect acute and chronic post-operative pain outcomes. Specifically, 150 male and female patients meeting study inclusion criteria and preparing to undergo TKA at the Penn Presbyterian Medical Center will be randomized to either receive the computer-assisted preoperative CBT intervention (n=75) or treatment-as-usual (control, n=75). The effectiveness of the intervention to address the preoperative risk factors for CPSP will be evaluated by comparing pain severity, opioid use, symptoms of depression, anxiety and pain catastrophizing before and following the 4-week pre-surgical period and compared within and across subjects. Post-operative pain severity will be abstracted from the electronic health record (EHR) and compared to post-operative pain severity ratings between the intervention and control groups. Similarly, group differences will be inspected for rates of CPSP at 3- and 6-months following surgery. In addition, due to the novelty of the CBT/opioid sparing intervention, brief (15-20min) qualitative interviews will be conducted with the participants who received it during the study visit immediately prior to surgery, to assess patient utilization, and satisfaction with the program in general, and the opioid taper component specifically; adherence is tracked by the PAINTrainer. Participants will be prompted to comment on the perceived ease of use, burden, helpfulness and quality of the CBT intervention.

A randomized clinical trial was designed because it provides the highest level of evidence and lowest risk for bias. The methods employed are predominantly quantitative, although a qualitative survey approach is used to assess subject satisfaction with the intervention. The project is designed, staffed and budgeted to be completed in 24 months. In consultation with consultants, [name] will train the study coordinator coach on delivering the opioid taper intervention during months 1-3, during which time study start-up activities will take place. Enrollment will begin month 3; at a rate of 12-13 enrollments per month, we anticipate having enrolled 166 subjects (n=150, assuming 10% attrition) by study month 15, providing adequate time for 3- and 6-month follow up, and dissemination activities.

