Pain catastrophizing – Pain catastrophizing will be measured by the Pain Catastrophizing Scale (PCS).⁵³ The PCS is a 13-item self-report scale, with each item rated on a 5-point scale: 0 (Not at all) to 4 (all the time). It is broken into three subscales (magnification, rumination, and helplessness); results from the initial development and validation studies indicate that the PCS is a reliable and valid measurement tool for catastrophizing in clinical and non-clinical populations. PCS will be completed prior to and following completion of the intervention and at the 3- and 6-month follow ups to assess the durability of the intervention.

Depression and Anxiety - To measure symptoms of depression and anxiety, the PROMIS® (Patient-Reported Outcomes Measurement Information System) person-centered measures will be utilized.⁵⁴ Specifically, the 8-item PROMIS depression and anxiety short forms will be compared prior to and following completion of the intervention; to evaluate the stability of CBT skills, the PROMIS will also be administered at 3 and 6 months.

Potential confounders – Pre-existing medical comorbidities or post-operative complications may affect surgical outcomes with respect to pain severity and resolution. To account for the effects of these confounders, all medical comorbidities will be extracted from the EHR by the study coordinator prior to surgery and recorded in the study database. Also added to the study database will be any unanticipated adverse events following surgery, and with medical comorbidities, considered as moderators of the effects of the intervention on the development of CPSP.

Post-operative pain intensity – Severity of post-operative pain will be operationalized as (1) responses on a visual analogue pain scale (VAS) and (2) consumption of opioid analgesic medications during the first 72 hours following surgery. The VAS ranges from 0 (no pain) to 10 (worst pain imaginable), and pain scores are collected every 4 hours as part of routine practice. Pain ratings will be graphed over time and area under the curve calculated. Dose of opioid analgesics consumed during this period (24hr increments and total) will be abstracted from the electronic health record and converted into MEDD for analysis.

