Opioid taper: As a part of the intervention and with the guidance of their trained coach, one-half of the subjects will be encouraged to gradually taper their opioid use in the month prior to surgery. It is possible that in doing so, subjects may experience the uncomfortable symptoms associated with opioid withdrawal. To avoid the emergence of these, subjects will be instructed to taper their dose gradually (no more than 10%/week), and will be provided with information on how to self-manage these symptoms should they arise. In addition, subjects will be instructed to contact their coach should the symptoms become severe, to receive guidance on how to temporarily cease and then restart taper attempts. In that subjects will have been regular users of opioids for at least three months prior to study enrollment, they will have developed a certain degree of physiologic tolerance, offering protection against any respiratory depressant effects during a taper pause.

Breach of Confidentiality: Participation in this study may constitute a social risk to the participant in that others may learn that he or she has chronic pain and is taking opioid medications. Due to the sensitive nature of this information, privacy and confidentiality will be strictly maintained in all aspects of participation. Consent and data collection sessions will take place in private rooms where strict privacy is enforced and all staff are HIPAA certified.

Acute Anxiety or Depressive Symptoms: It is possible that the opioid taper for the intervention group, or the upcoming surgery for both groups may precipitate unanticipated symptoms of acute anxiety or depression. As described below, co-PI [name] is a licensed clinical psychologist with over 40 years' experience in treating patients with chronic pain, will be available to assess and intervene with patients who experience these distressing symptoms during the pre-operative period.

2. Benefits:

The potential benefit for both the participants and broader segments of society is to improve pain outcomes following a very common procedure, TKA, ideally decreasing the severity of post-operative pain experienced and

the development of CPSP. Development of an effective intervention to address the risk factors for poor pain outcomes following TKA can guide clinical practice based upon evidence.

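### Worsening anxiety or depression is a named risk, but the plan has no by-arm summary of it, so harm in a minority could sit behind a favourable mean change

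*Combined protocol and SAP*

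**What the plan says.** **The risk.** RISK/BENEFIT ASSESSMENT, 1. Risks, has an entry on acute anxiety or depressive symptoms. It gives two possible causes: the taper, which only the intervention arm is coached to attempt, and the coming operation, which both arms face. Either "may precipitate unanticipated symptoms of acute anxiety or depression".

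**The measurements.** METHODS, 1. Study Instruments, says that "the 8-item PROMIS depression and anxiety short forms will be compared prior to and following completion of the intervention", with repeats at 3 and 6 months to see whether the CBT skills last. The schedule places PROMIS at T-4 weeks, T0, and 3 and 6 months.

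**The analysis.** STUDY PROCEDURES, 5. Statistical Analysis, lists depression and anxiety among the second-objective outcomes expected to improve more with the intervention. They go into a mixed model, and "The results from the mixed model analyses will be summarized by mean (SE) change from baseline for each group at each time point". It adds that "sensitivity analyses will be run considering dichotomous versions of the outcome variables using multiple logistic regression", but gives no cut-point and does not say whether improvement or worsening is counted.

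**The safety provisions.** Data and Safety Monitoring provides psychologist assessment after a high depression score or extreme distress. It also sends the DSMB the number, severity and relatedness of adverse events, and the reasons for attrition. Early Withdrawal of Subjects lists extreme anxiety or depression as a safety ground for withdrawal.

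**The concern.** The intervention joins a component meant to lower distress (CBT) to one that the protocol says may raise it in some patients (the taper). A mean change adds the two together. If most patients improve and a few get clearly worse, the arm mean can still look favourable, and neither the mean nor its SE shows how many worsened.

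The other provisions do not supply that count by arm:

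- The dichotomous analysis might, but as an improved-or-not split it would pool unchanged patients with worse ones. The text does not say which split is meant.
- Psychologist review is individual care and has no stated score threshold.
- The DSMB reports are not said to be by arm, and nothing says that a PROMIS rise is recorded as an adverse event.
- The adverse events that Study Instruments adds to the database are those after surgery, for use as moderators of CPSP. The taper comes before surgery.

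Withdrawal for extreme distress may also leave the worst-affected patients without a T0 score. The stated goal is to inform larger studies, and these would start with an incomplete picture of a harm the protocol itself foresaw.

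**Working it through.** **Inputs**

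- 75 per arm: STUDY DESIGN.
- Effect size 0.33, 80% power, alpha 0.05: power paragraph under Target Population and Accrual. The 0.33 is stated for chronic pain severity; using it for PROMIS is an assumption.
- PROMIS SD, worsening rate and worsening margin: not given. All values below are assumed, in SD units.

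**1. The plan's own figure.** Sidedness is not stated; two-sided is assumed. For a paired pre-post test, n = ((1.960 + 0.842)/0.33)² = 72.1, rounded up to 73. The paired t version gives 74.02, rounded up to 75, with 80.5% power at n = 75. The stated 75 is therefore reproduced. It is sized for a within-group mean improvement and says nothing about the proportion who worsen.

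**2. How much worsening a mean can hide.** Let a fraction f of the intervention arm worsen by h SD and the rest improve by g SD.

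Mean improvement M = (1 − f)g − fh, which is zero at f = g/(g + h).

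With g = 0.33:

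| h (SD) | Break-even f | Of 75 patients |
|---|---|---|
| 0.5 | 0.33/0.83 = 0.40 | 29 |
| 1.0 | 0.33/1.33 = 0.25 | 18 |
| 1.5 | 0.33/1.83 = 0.18 | 13 |

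The last column is the largest whole number of patients for which the mean still shows improvement. At h = 1:

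- f = 0.10: M = 0.9 × 0.33 − 0.10 = 0.197, a benefit
- f = 0.20: M = 0.8 × 0.33 − 0.20 = 0.064, a benefit
- f = 0.30: M = 0.7 × 0.33 − 0.30 = −0.069, no longer a benefit

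This concerns the intervention arm's own mean. The contrast with control also depends on how control patients change before surgery.

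**3. Effect of withdrawal.** Take f = 0.20 and h = 1: 60 patients improve by 0.33 SD and 15 worsen by 1 SD. The full mean is (60 × 0.33 − 15)/75 = 4.8/75 = 0.064. If 5 of the 15 are withdrawn and have no T0 score, the raw mean of observed changes is (19.8 − 10)/70 = 0.14. The summary looks better because the worst cases are absent.

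**4. Precision of a count of worsening.** For 15% v 5% at 75 per arm, the difference is 10 points.

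SE = √(0.15 × 0.85/75 + 0.05 × 0.95/75) = 0.0483, and 1.96 × 0.0483 = 0.095, or about ±9.5 points.

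Power is 53% for 5% v 15% and 80% for 5% v 20%. Such a table is descriptive, not a powered test.

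**5. Whether the control comparator exists.** STUDY DESIGN says that both groups provide pre-operative data, and the schedule limits only the CBT use and satisfaction row to the treatment group. The pre-operative session in STUDY PROCEDURES describes the repeat assessments for the experimental group alone. These must agree before any by-arm comparison at T0 is possible.

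**The case against.** The strongest reply is that safety is not neglected. A high depression score triggers review by a psychologist, adverse events and attrition reasons go to the DSMB, and weekly reports cover health events. The trial is a small pilot with exploratory contrasts, and a worsening table would be imprecise. All of this stands, and it limits the point to a reporting gap. What remains is that none of these routes is stated to compare the arms, and milder worsening may not enter them.

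A reader might infer four stronger things that the documents do not support:

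- *The scores are analysed only by mean change and have only an efficacy use.* The dichotomous analyses are also planned, though undefined, and a high depression score is a safety trigger.
- *No planned output could show the harm.* DSMB reports could show severe cases and withdrawals.
- *Harm would be reported as benefit.* This depends on assumed inputs. With g = 0.33 and h = 1, 25% worsening gives 0.75 × 0.33 − 0.25 = −0.0025, no benefit.
- *Patients who worsen were harmed by the taper.* The risk section also names the coming surgery in both arms, so worsening in one patient at T0 cannot be attributed to the taper. Only a comparison by arm can help separate the two.

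It is also fair to say that PROMIS at T-4 weeks and T0 can miss acute distress that comes and goes during the taper. The table proposed here does not repair that.

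**Conclusion.** The point holds as a gap in the planned reporting of harm. The protocol names acute anxiety or depression as a possible effect of the taper and of surgery and collects scores that bear on it. It then plans to summarise them by mean change, with an undefined dichotomous analysis and no stated by-arm account of worsening, psychological adverse events or distress withdrawals. Worsening in a minority could be hidden, and withdrawals could add to this.

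How large the effect might be cannot be known from the documents. The break-even share of about 25% assumes that worsening patients lose 1 SD and that the rest gain 0.33 SD, a value borrowed from pain severity. Across assumed worsening of 0.5 to 1.5 SD, the share runs from 40% down to 18%. This is a worthwhile, inexpensive improvement; it does not invalidate the efficacy analysis.

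**What to change.** Add a short paragraph to Statistical Analysis specifying a descriptive safety summary by assigned arm, for PROMIS depression and anxiety separately:

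- the distribution of individual changes from baseline to T0, as a cumulative plot by arm;
- the number and proportion worsening by more than a margin fixed before any by-arm data are seen, with risk difference and 95% CI;
- patients withdrawn for anxiety or depression counted as worsened, with the number of other missing T0 scores shown by arm;
- psychological adverse events and distress withdrawals tabulated by arm;
- any 3- and 6-month repeat labelled descriptive, since it follows surgery.

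Report it as harm data whatever the mean shows, and do not attribute individual cases to the taper. State the cut-point and direction of the dichotomous sensitivity analysis. Reconcile the pre-operative session text with STUDY DESIGN and the schedule, so that it is clear that control patients give T0 scores.

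The cost is one paragraph, one table and one plot from data the plan already collects, with no new visits and no change to clinical care. The limits are modest precision (about ±9.5 points in the example) and no view of transient distress between T-4 weeks and T0.
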